7.1. General Considerations

7.1.1. Overall

The statistical analyses will be reported using summary tables, figures and listings (TFLs). Numbering for TFLs will be based on the recommended numbering convention provided by the International Council for Harmonisation (ICH). All summary tables will be presented by treatment group. Listing of Screen Failures will also be presented based on Eligibility Criteria (Inclusion/Exclusion) not met. Select baseline tables may also include a total column summary. Tables and listings will be presented in RTF format.

Continuous (quantitative) variable summaries will include the number of subjects (n) with non-missing values, mean, standard deviation (SD), median, minimum, maximum and quartiles. Categorical (qualitative) variables will be summarized by frequencies and percentages of subjects in corresponding categories. The denominator for the percentage calculation will be based upon the total number of subjects in the study population for the treatment or sequence group with non-missing data for the variable of interest.

The minimum and maximum will be reported with the same degree of precision (i.e., the same number of decimal places) as the observed data. Measures of location (mean and median) will be reported to one degree of precision more than the observed data and measures of spread (standard deviation) will be reported to two degrees of precision more than the observed data.

Percentages will be presented to one decimal place unless otherwise specified. Assessments done on unscheduled visits will not be summarized but will be listed.

P-values ≥ 0.001 will be reported to four decimal places; P-values less than 0.001 will be reported as “<0.001”.

For analysis purposes, repeat laboratory test results will not be used unless the original laboratory value is missing or indicated as invalid, in which case the first non-missing repeat laboratory value will be used for data analysis.

All collected data will be presented in listings and will be sorted by subject. CDISC-compliant datasets (STDM and ADAM) will also be provided to the sponsor.

7.1.2. Safety Analysis

The Safety Set population will be used for all summaries of Adverse Events (AEs), Pre-Treatment Adverse Events (PTEs), TEAEs, laboratory tests, and vital signs. All safety data will be summarized by treatment.

AEs will be presented in listings. TEAEs will be classified according to system organ class and preferred term and will be tabulated with a breakdown by treatment and by event severity. Similar TEAE tabulations will be performed on those events assessed by the investigator as related to study drug.

Individual results of vital signs will be listed and observed values and changes from Baseline in vital signs will be summarized by treatment.

Physical exam findings, suicidality assessments (C-SSRS), PANSS scores, Diagnostic Screening results and pregnancy test results will be presented in subject-level listings.

7.1.3. Pharmacokinetic Analysis

Blood samples will be collected for the determination of plasma concentration of CVN058, and its metabolite if appropriate, at the following time-points: Pre-dose (within 15 minutes prior to dosing), and a one (1) hour (pre-EEG) and five (5) hours (post-EEG) post-dose. The plasma concentration data (parameters C_{max}, t_{max} and AUC (0 to 5 hrs.) will be summarized over each scheduled sampling interval using descriptive statistics (arithmetic mean, SD, median, minimum and maximum). Individual plasma concentration data versus time will be presented in a data listing.

Descriptive statistics will be used to summarize the plasma PK parameters for CVN058, and its metabolite if appropriate. In addition, geometric mean and percent coefficient of variation will be computed for C_{max} and AUC_t.

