2.2. Clinical

Two human clinical studies of CVN058 have been completed (ENV8058_101 and TAK-058-1002).

CVN058 is orally absorbed and readily passes the blood brain barrier, allowing it to occupy cortical 5-HT3 receptors. In study ENV8058_101, CVN058 was well tolerated up to a dose of 150 mg administered orally as a single dose in aqueous solution. There were no deaths or other serious adverse events (SAEs) reported in this study and no subject discontinued study due to a treatment-emergent adverse event (TEAE). There were no clinically significant laboratory abnormalities, electrocardiogram (ECG) changes or changes in vital signs in the completed single dose study.

The mean C_{max} and area under the plasma concentration–time curve (AUC) values of CVN058 increased less than proportionally with increasing CVN058 dose across the dose range of 5 to 150 mg, but mean C_{max} and AUC values increased in an approximately dose proportional manner across the 5 to 45 mg dose range. The rate of appearance of CVN058 in plasma was rapid with median time to C_{max} (t_{max}) values of 1 to 1.25 hours across the dose range of 5 to 150 mg. The mean terminal elimination half-life ($t_{1/2z}$) values of CVN058 ranged from approximately 2.8 to 10.5 hours across the cohorts; the lower doses (5 to 30 mg) had lower mean $t_{1/2z}$ values compared to the higher doses (45 to 150 mg). There were no trends with mean apparent clearance values of CVN058 with increasing dose from 5 to 45 mg, but faster apparent clearance was observed at the 75 and 150 mg doses, possibly due to decreased bioavailability (BA) at higher doses. The mean apparent volume of distribution (Vz/F) increased as dose increased. Excretion of unchanged CVN058 in the urine was $\leq 2.3\%$ of the administered CVN058 dose over the dose range evaluated.

In the multiple-rising dose study (TAK-058-1002), CVN058 was well-tolerated at daily doses of 25, 75, and 150 mg for 7 days, and at a single 300 mg dose, in aqueous solution. There were no deaths or other SAEs reported in this study and no subject discontinued study due to a TEAE. There were no clinically significant laboratory abnormalities, ECG changes or changes in vital signs in the completed single dose study. Following single or multiple doses, the mean C_{max} and

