4.3. Study Design Summary

In the initial study design, subjects were randomized to 1 of 6 treatment sequences to receive 1 of 3 dose regimens in each period. Each dose regimen consisted of a single oral administration of CVN058 (15 mg or 150 mg initially) or a matching placebo; study drug to be administered with water in the morning. The sequence will determine the order in which a subject will receive each of the 3 regimens. Discontinued subjects may be replaced so that 20 completed subjects are available for analysis.

After the Interim Analysis, the 15 mg dose in each treatment sequence was replaced with a 75 mg dose under Protocol Amendment 4, applicable to all subjects randomized.

Each treatment period is less than 1 day in duration, with a minimum of 7-day washout, maximum 10-day washout between doses. A follow-up telephone call will occur approximately 7-10 days following the last dose received. Subjects may be inpatients or outpatients at the discretion of the Investigator.

At each testing session, subjects will undergo post dose EEG testing including: MMN, P50, qEEG, gamma power, and P300. Testing sessions will begin approximately 1.5 hours post-dose. Prior to dose and at various time points post-dose, blood samples will be collected for the assessment of plasma concentrations of CVN058 and biomarkers.

Study procedures will be conducted at approximately the same times across Treatment Periods to minimize diurnal effects on outcomes. The effect of CVN058 on MMN as well as on exploratory measures (e.g., P50 auditory gating, gamma power, and P300) will be compared to placebo.

5. Determination of Sample Size

Enrollment of at least 20 subjects with schizophrenia (including schizoaffective disorder) is estimated to provide >80% power to detect a median effect size of Cohen's $d=0.5$. Discontinued or withdrawn subjects and subjects for whom MMN is not available for all three study periods may be replaced. The sample size chosen of at least 20 completed subjects is considered to be sufficient to explore the changes in MMN between CVN058 and placebo as well as safety and tolerability of CVN058 in this population. There will be approximately three (3) study sites in the United States. The sample size is subject to re-estimation based on preliminary data.

The sample size re-estimation will occur after twelve (12) subjects have completed all study visits. Full details are discussed in [Section 8](#).

6. Analysis Populations

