12.1. Planned Tables

Table Number	Table Title
14.1.1.1	Subject Disposition by Treatment Sequence and Overall (All Subjects)
14.1.1.2	Subject Disposition by Dose Level and Overall (All Subjects)
14.1.2.1	Demographics and Baseline Characteristics by Treatment Sequence and Overall (All Subjects)
14.1.2.2	Demographics and Baseline Characteristics by Dose Level and Overall (All Subjects)
14.1.3.1	Medical History by Dose Level and Overall (All Subjects): Reported at Baseline
14.1.3.2	Medical History by Dose Level and Overall (All Subjects): Ongoing
14.2.1.1	Primary Analysis: MMN Improvement (CVN058 vs. Placebo), Summary Statistics and Modeling Summary of Amplitude of Duration MMN (PD) by Dose Level
14.2.2.1	Secondary Analysis: Summary of Subject Adverse Events (SAF) by Most Recently Administered Dose Level and Overall
14.2.2.2	Treatment-Emergent Adverse Events by SOC and PT (SAF) by Most Recently Administered Dose Level and Overall
14.2.2.3	Serious Treatment-Emergent Adverse Events by SOC and PT (SAF) by Most Recently Administered Dose Level and Overall
14.2.2.4	Treatment-Emergent Adverse Events by Severity, SOC and PT (SAF) by Most Recently Administered Dose Level and Overall
14.2.2.5	Treatment-Emergent Adverse Events by Relationship to Study Drug (SAF) by Most Recently Administered Dose Level and Overall
14.2.3.1	Secondary Analysis: Summary of Clinically Significant Abnormal Laboratory Test Results (SAF) by Most Recently Administered Dose Level and Overall
14.2.3.2	Summary of Hematology Laboratory Data (SAF) Overall
14.2.3.3	Summary of Chemistry Laboratory Data (SAF) Overall
14.2.3.4	Summary of Urinalysis Laboratory Data (Continuous Variables) (SAF) Overall
14.2.3.5	Summary of Urinalysis Laboratory Data (Categorical Variables) (SAF) Overall
14.2.4	Summary of Vital Signs and Body Measurements (SAF) by Most Recently Administered Dose Level and Overall
14.2.5.1	Pharmacokinetic Analysis: Summary at Scheduled Sampling Intervals (PK) by Dose Level
14.2.5.2	Pharmacokinetic Analysis: Summary of PK Parameters (PK) by Dose Level
14.2.5.3.1	Pharmacodynamic Analysis: Summary of P50 Ratio (S2/S1) (PD) by Dose Level
14.2.5.3.2	Pharmacodynamic Analysis: Summary of P50 Differences (S2-S1) (PD) by Dose Level
14.2.5.3.3	Pharmacodynamic Analysis: Summary of Pre-stimulus Gamma Amplitude (PD) by Dose Level
14.2.5.3.4	Pharmacodynamic Analysis: Summary of P300 Amplitude (PD) by Dose Level
14.2.5.3.5	Pharmacodynamic Analysis: Summary of P300 Latency (PD) by Dose Level

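### With post-dose samples only at 1 h and 5 h, the planned tmax can only return a draw time, Cmax is the larger of two values, and two different AUCs share one summary (minor)

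*SAP*

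**What the plan says.** SAP section 7.1.3 fixes three samples per period: "Pre-dose (within 15 minutes prior to dosing), and a one (1) hour (pre-EEG) and five (5) hours (post-EEG) post-dose". Section 4.3 speaks more loosely of various post-dose times and says of the EEG: "Testing sessions will begin approximately 1.5 hours post-dose". The two post-dose draws therefore bracket the EEG session.

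From these samples, section 7.1.3 plans: "The plasma concentration data (parameters C_{max}, t_{max} and AUC (0 to 5 hrs.) will be summarized over each scheduled sampling interval". It then adds that "geometric mean and percent coefficient of variation will be computed for C_{max} and AUC_t". Section 12.1 lists the output as Table 14.2.5.2, "Pharmacokinetic Analysis: Summary of PK Parameters (PK) by Dose Level".

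The glossary defines Cmax as the highest observed concentration, and AUC_t as the area up to the last concentration that could be quantified.

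For the earlier single-dose study, section 2.2 gives median tmax "values of 1 to 1.25 hours across the dose range of 5 to 150 mg", and says that mean terminal half-life "values of CVN058 ranged from approximately 2.8 to 10.5 hours across the cohorts".

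**The concern.** A parameter that can take only two values, both set by the schedule, is not an estimate of when the drug peaks. A reported median tmax of 1 h would look like confirmation of the earlier 1 to 1.25 h, although the draw times alone would produce it for a wide range of true peaks. Cmax has a milder form of the same problem, since nothing is measured between 1 h and 5 h.

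The AUC wording raises a separate issue. AUC (0 to 5 h) and AUC_t are the same only when the 5 h concentration is available and quantifiable. Otherwise AUC_t stops at 1 h, and as written that short area enters the same geometric mean and CV as the full ones.

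At stake is the reading of one descriptive table, not a test or a decision.

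**Working it through.** **1. tmax (no model needed).** The post-dose draws are at nominal 1 h and 5 h. Observed tmax is the time of the larger value, so it is 1 h if C1 ≥ C5 and 5 h otherwise. No other value is possible, apart from small deviations in actual draw time.

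**2. Cmax and AUC(0-5) under an assumed model.**

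- From SAP section 2.2: half-life 2.8 to 10.5 h (6 h added as a midpoint) and median tmax 1 to 1.25 h.
- Assumed, not in the SAP: one compartment with first-order absorption, and individual tmax from 0.5 to 3 h.
- Pre-dose concentration is taken as zero. The minimum 7-day washout is 168/10.5 = 16 of the longest half-lives.

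Formulas: ke = ln 2 / half-life; ka solved from tmax = ln(ka/ke)/(ka − ke); C(t) = ka/(ka − ke) × (e^(−ke·t) − e^(−ka·t)), scaled to unit dose/volume. Linear trapezoid: AUC(0-5) = 0.5·C1 + 4·(C1 + C5)/2 = 2.5·C1 + 2·C5.

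Example, tmax 1.25 h and half-life 2.8 h:

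- ke = 0.2476 and ka = 1.862.
- C1 = 0.721, true peak 0.734, C5 = 0.334. Observed/true Cmax = 0.721/0.734 = 0.983.
- Trapezoid = 2.5 × 0.721 + 2 × 0.334 = 2.47, against a true area of 2.69. The ratio is 0.919.

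Ranges over the three half-lives:

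| True tmax | Recorded tmax | Observed/true Cmax | Linear AUC/true AUC(0-5) |
|---|---|---|---|
| 0.5 h | 1 h | 91.5–97.4% | 90.8–92.9% |
| 1 h | 1 h | 100% | 93.0–94.5% |
| 1.25 h | 1 h | 98.3–99.1% | 91.9–93.1% |
| 2 h | 1 h | 83.8–89.2% | 84.3–90.4% |
| 2.5 h | 5 h | 75.9–89.3% | 82.6–88.3% |
| 3 h | 5 h | 86.1–93.0% | 82.7–86.9% |

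True peaks from 0.5 to 2 h are all recorded as 1 h, and peaks at 2.5 to 3 h as 5 h. With biphasic disposition (assumed) and tmax 1 to 1.25 h, observed Cmax is 97.8–100% of true and linear AUC 92–101%.

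**3. AUC_t when the 5 h value is missing or unquantifiable.** AUC_t is then 0.5·C1. With r = C5/C1, its share of the 0 to 5 h trapezoid is 0.5/(2.5 + 2r).

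- Lowest r in the runs (tmax 0.5 h, half-life 2.8 h): r = 0.340/0.915 = 0.372; share = 0.5/3.243 = 15.4%.
- Highest r (tmax 3 h, half-life 2.8 h): r = 0.861/0.653 = 1.319; share = 0.5/5.137 = 9.7%.
- Without any model: r = 0 gives 20% and r = 1 gives 11%.

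As an illustration, take 20 subjects, one of whom contributes 15% of the area that he or she should. The geometric mean is multiplied by 0.15^(1/20) = 0.91, so one such subject lowers it by about 9%. The SAP gives no quantification limit or expected rate of missing samples, so how often this would happen is unknown.

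**The case against.** The strongest reply is that little depends on these parameters. The primary MMN analysis uses no PK. All ten exposure-response scatterplots (Figures 16.3.6.4.1.1 to 16.3.6.4.5.2) already use the measured 1 h or 5 h concentration. Table 14.2.5.1 summarises PK at the scheduled sampling times, Listing 16.2.10 gives individual values, and no PK test is planned. All of this stands. A reader might infer that the exposure-response objective is compromised, but the planned figures do not support that.

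A reader might also infer that the schedule misses a peak at 1 to 1.25 h. It does not: the 1 h draw then recovers 98–100% of the peak. At that tmax the AUC shortfall is about 5 to 8% in the one-compartment model and nearly the same at every half-life, so a ratio between doses would move by at most about 3% (0.945/0.919 = 1.028). The larger errors in the table need individual peaks well away from 1 h, and section 2.2 gives medians only.

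Finally, the glossary's Cmax is by definition the observed maximum, and AUC_t equals AUC(0-5) whenever the 5 h value is quantifiable. With the stated half-lives, 37 to 77% of the 1 h concentration would remain at 5 h under log-linear decline (2^(−4/2.8) and 2^(−4/10.5)), so an unquantifiable 5 h value may be rare. That lowers the likelihood, but it does not cover a missing sample or make the two AUC labels agree.

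None of this rescues tmax.

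**Conclusion.** The point holds as a minor correction.

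- **tmax:** uninformative by construction. This needs no assumption beyond the stated draw times.
- **Cmax:** only the larger of two concentrations. It is within about 2% of the true peak if a subject peaks at 1 to 1.25 h. The shortfall reaches about 24% only at the edge of an assumed individual spread of 0.5 to 3 h.
- **AUC:** section 7.1.3 uses two labels for quantities that differ when the 5 h value is absent or unquantifiable. Such a subject would contribute about 10 to 15% of the intended area.

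It would go too far to conclude that all the PK parameters are misleading. That is established for tmax only. For Cmax and AUC it depends on a spread of individual peak times that the SAP does not report.

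**What to change.** In section 7.1.3 and the shell for Table 14.2.5.2:

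1. Drop tmax.
2. Report the 1 h (pre-EEG) and 5 h (post-EEG) concentrations by dose, with geometric mean and CV. Drop Cmax, or label it as the larger of the two post-dose samples.
3. Replace AUC_t by AUC(0-5 h) throughout. Calculate it by the linear trapezoid, only in subjects with both post-dose concentrations available and quantifiable. Label it an approximate partial area and give the number of subjects left out.

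The cost is SAP wording and one table shell, with no additional blood draws. The downside is that a conventional tmax, and possibly Cmax, is no longer reported from this study. The primary analysis and the exposure-response figures stay as they are.

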7.1.4. Pharmacodynamic Analysis

In general, observed values for the PD parameters (MMN and exploratory PD parameters [P50, qEEG and P300]) in each treatment period will be summarized by treatment and compared to time-matched placebo assessments using summary statistics. Summaries presented will include difference values (CVN058 – placebo).

7.1.4.1 Primary Analysis

The Primary Endpoint analysis will be performed on the PD population and will consist of a comparison of the post dose PD parameter Mean Amplitude of Duration MMN versus the parameter at time-matched placebo period timepoints using Generalized Linear Models with factors for sequence, subject nested within sequence, period, site and treatment. Two-sided 80% confidence intervals will be constructed for the least squares mean differences between CVN058 and placebo in PD parameters at the post-dose time point for each treatment period.

To maintain overall control of alpha (Type I error rate), the Primary Analysis will employ sequential testing, beginning with the higher dose (e.g., CVN058 150 mg) vs. Placebo using alpha = 0.10 and one-sided significance testing. If significant results are obtained from that first comparison, sequential significance testing of the next lower dose or doses (e.g., CVN058 75 mg) vs. Placebo will then be performed. If the first comparison yields a non-significant result, testing of the latter vs. Placebo will be performed to generate a nominal p-value, but that result will not be formally statistically significant regardless of the p-value.

Effect size will be calculated and summarized for comparisons of CVN058 to Placebo using Cohen's d which expresses the difference between the means of two groups as a function of their pooled standard deviation.

Exposure-response relationships for CVN058 will be explored graphically.

7.1.4.2 Exploratory Analyses

Exploratory endpoint analyses will consist of a comparison of each exploratory post-dose PD parameter versus the same parameter at time-matched placebo period timepoints using Generalized Linear Models and including factors for sequence, subject nested within sequence, period, site and treatment. Two-sided 80% confidence intervals will be constructed for the least squares mean differences between CVN058 and placebo in changes of PD parameters at the post-dose time point.

There will be no adjustment to maintain overall control of alpha (Type I error rate) for exploratory endpoints.

Effect sizes will be calculated and summarized for comparisons of CVN058 to placebo using Cohen's d which expresses the difference between the means of two groups as a function of their pooled standard deviation.

Exposure-response relationships for CVN058 will be explored graphically.

7.1.5 Adjustments for Covariates

Randomization for this study will be stratified by the study site in which subjects are enrolled. The model for the primary analysis will include this stratification variable as a main effect. This stratification variable may also be included as a factor for select secondary variables. Baseline values will also be used as a covariate when baseline is available for the endpoint.

7.1.6 Testing

Unless noted otherwise, all statistical tests will be one-sided with a significance level of $\alpha = 0.10$. Tests will be declared statistically significant if the calculated p-value is < 0.10 .

The analyses described in this plan are considered a priori, in that they have been defined prior to database lock. Any additional analysis performed after database lock will be considered post-hoc and exploratory. Post-hoc analyses will be labeled as such on the output and identified in the CSR.

All analyses and tabulations will be performed using SAS® version 9.4. Upon completion, all SAS programs will be validated by an independent programmer. The validation process will be used to confirm that statistically valid methods have been implemented and that all data manipulations and calculations are accurate. Checks will be made to ensure accuracy, consistency with this plan, consistency with tables, and consistency between tables and corresponding data listings.

7.1.7 Baseline Values

Unless otherwise noted, baseline is defined as the Period 1 – Day 1 (pre-dose) value recorded prior to the first study treatment. However, the baseline value for clinical laboratory assessments is defined as Visit 1 - Screening Day-28 for Hematology, Serum Chemistry, Urinalysis and Coagulation. If a baseline value is missing, the last non-missing value prior to the first study

treatment will be used. When applicable, unscheduled visits will be used in the determination of baseline values.

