11.3. Vital Signs and Body Measurements

Data from vital signs and body measurements (see below) will be listed. Observed values and change from baseline will be summarized by treatment group. Variables to be summarized are:

Variable
Heart Rate
Diastolic Blood Pressure

Systolic Blood Pressure

Respiratory Rate

Temperature

Weight

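### Vital-sign changes by dose are measured from the Period 1 pre-dose value in all three crossover periods, which adds avoidable spread to a descriptive safety table

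*SAP*

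**What the plan says.** - **Baseline.** SAP 7.1.7 takes as default the Period 1 "Day 1 (pre-dose) value recorded prior to the first study treatment". The one stated exception is that "the baseline value for clinical laboratory assessments is defined as Visit 1 - Screening Day-28 for Hematology, Serum Chemistry, Urinalysis and Coagulation". The missing-value rule is also study-level: "If a baseline value is missing, the last non-missing value prior to the first study" treatment is used. Vital signs are not excepted here or elsewhere.
- **Summaries.** SAP 7.1.2 says that "observed values and changes from Baseline in vital signs will be summarized by treatment". SAP 11.3 repeats it: "Observed values and change from baseline will be summarized by treatment group". Table 14.2.4 in SAP 12.1 is titled "Summary of Vital Signs and Body Measurements (SAF) by Most Recently Administered Dose Level and Overall".
- **Design.** In SAP 4.3, "subjects were randomized to 1 of 6 treatment sequences to receive 1 of 3 dose regimens in each period". Each regimen is one oral dose, each period lasts less than a day, and periods are spaced "with a minimum of 7-day washout, maximum 10-day washout between doses".

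**The concern.** The acute effect of a single dose on heart rate or blood pressure is naturally read as the change from the reading just before that dose. Under 7.1.7 this holds only in Period 1. In Periods 2 and 3, about two thirds of the changes in subjects who complete the study, the reference is a reading from an earlier visit. The printed change for a dose then combines what happened after dosing with how that person differed between visits one to three weeks apart.

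At stake is the legibility of one descriptive table that supports the secondary objective on safety and tolerability of single doses (SAP 3.1.2). Extra spread makes a modest acute change harder to see, and a general drift over visits would appear inside each dose's mean change. SAP 7.1.2 and 11.3 plan each treatment's own change and no placebo-subtracted vital-sign summary, so the plan itself does not remove that component.

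**Working it through.** The SAP states no figure on this point, so there is none to reproduce.

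**1. Age of the baseline.** Input: 7 to 10 days between doses (SAP 4.3).
- Period 2: 7 to 10 days (1.0 to 1.4 weeks).
- Period 3: 2 × 7 = 14 to 2 × 10 = 20 days (2.0 to 2.9 weeks).

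**2. Spread of the change in Periods 2 and 3.** Assumptions, none from the SAP: equal SD at every reading; correlation *rb* between readings at different visits, 0.5 (range 0.4 to 0.6); correlation *rw* between pre- and post-dose readings at one visit, 0.75 (range 0.7 to 0.8). In units of SD²:
- Period 1 baseline: variance = 2(1 − rb)
- same-period baseline: variance = 2(1 − rw)
- SD ratio = √[(1 − rw)/(1 − rb)] = √(0.25/0.5) = 0.707, a 29% cut. The range runs from √(0.3/0.4) = 0.866 (13%) to √(0.2/0.6) = 0.577 (42%).

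**3. Spread in the table as planned.** Table 14.2.4 groups by dose. With sequences equally filled and completed, one third of each dose's records come from Period 1, where the two baselines coincide. Leaving drift out:
- pooled variance, current rule = (1/3)·2(1 − rw) + (2/3)·2(1 − rb)

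| rw | rb | current rule | same-period | SD ratio | cut in SD |
|---|---|---|---|---|---|
| 0.75 | 0.5 | (0.5 + 2 × 1.0)/3 = 0.833 | 0.5 | √(0.5/0.833) = 0.775 | 23% |
| 0.7 | 0.6 | (0.6 + 2 × 0.8)/3 = 0.733 | 0.6 | √(0.6/0.733) = 0.905 | 10% |
| 0.8 | 0.4 | (0.4 + 2 × 1.2)/3 = 0.933 | 0.4 | √(0.4/0.933) = 0.655 | 35% |

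A simulation agrees. With an assumed within-visit SD of 5 units, between-visit SD of 5 and drift of 1 unit per period, the pooled SD of change was 9.17 with the Period 1 baseline and 7.07 with the same-period baseline: 7.07/9.17 = 0.771, again a 23% cut.

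**4. Drift in the mean.** Assume drift of 0, D and 2D in Periods 1, 2 and 3 and no drug effect.
- With 18 subjects spread equally over six sequences, each dose's mean change contains (0 + D + 2D)/3 = 1.0 D. With a same-period baseline it contains 0.
- Add two subjects in the least favourable pair of sequences (N = 20). One dose carries (18 + 4)/20 = 1.10 D and the other two (18 + 1)/20 = 0.95 D. The largest difference between doses is 0.15 D.

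**5. Dose minus placebo within subject.** With a shared baseline B, (Y_dose − B) − (Y_placebo − B) = Y_dose − Y_placebo, so B cancels.
- Shared baseline: variance = 2(1 − rb).
- Same-period baselines, with all cross-period correlations equal to rb: variance = 4(1 − rw).
- Central values: 1.0 against 1.0, no gain.
- rw 0.8, rb 0.4: 1.2 against 0.8; √(0.8/1.2) = 0.82, an 18% smaller SD.
- rw 0.7, rb 0.6: 0.8 against 1.2; √(1.2/0.8) = 1.22, a 22% larger SD.

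**The case against.** The other side has a good deal of weight.

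- **A single untreated baseline is defensible.** The Period 1 value precedes all study drug and is a recognised choice for descriptive safety tables. This stands for overall changes. It fits less well for the acute change after a single dose in a period of under a day.
- **Dose-versus-placebo comparison.** A reader might infer that the rule biases the comparison of active doses with placebo. The design in SAP 4.3 does not support that: balanced sequences give every dose the same drift, the placebo column shows it, and even an uneven N = 20 leaves only 0.15 D. Dropout, replacement and the change of the lower dose after the interim analysis could disturb the balance, but no material bias is shown. Step 5 also shows that the contrast would not reliably gain precision from the change. Both points stand.
- **Size.** A reader might apply the 29% to the whole table. It describes Period 2 and 3 records only; the pooled figure is 23%.
- **Weight.** The secondary endpoints in SAP 3.2.2 are the percentages of subjects with a TEAE and with a clinically significant abnormal laboratory result. Neither uses this baseline. No vital-sign test is planned, observed values stand beside the changes, and individual readings are listed (Listing 16.2.8.2). This stands and limits the severity.
- **Attribution.** The title of Table 14.2.4 invites the inference that a later period's pre-dose reading is filed under the previous dose. It is only a title: the SAP does not say that time points are pooled, and rows by time point would avoid this. It calls for clarification and is not an established error.
- **Carry-over into a later baseline.** This is unlikely to matter. The longest mean half-life in SAP 2.2 is about 10.5 hours, and 7 days is 168 hours: 168/10.5 = 16 half-lives.
- **Feasibility.** The SAP gives no vital-sign schedule. It does place blood sampling before dosing (SAP 4.3 and 7.1.3), so subjects are seen then, but pre-dose vital signs in each period need confirming in the protocol.

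**Conclusion.** The point holds as a minor one. SAP 7.1.7 states a rule that gives a less informative per-dose change than the design allows: Period 2 and 3 changes are taken from a value 7 to 20 days old. The cost is extra between-visit spread, plus any drift, in each dose's own mean change. A same-period baseline would reduce the pooled by-dose SD of change by about 23% (10% to 35%).

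That figure rests on assumed correlations, equal SDs across readings, and sequences equally filled and completed. If vital signs correlated as closely between visits as within a visit, there would be no gain. The finding is confined to a descriptive safety table. The primary MMN analysis, the named secondary endpoints and all planned tests are untouched.

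**What to change.** - **SAP 7.1.7:** where pre-dose vital signs are collected in each period, define the baseline for by-dose vital-sign changes as the Day 1 pre-dose value of that period, using the Period 1 value only if it is missing. Keep the Period 1 baseline for the overall column.
- **Table 14.2.4:** specify that a pre-dose reading of a later period is not counted as a post-dose reading of the previous dose.
- **Keep the observed values beside the changes.** A dose-minus-placebo contrast of changes could be somewhat noisier with period-specific baselines, and the observed values allow that contrast without them.

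The cost is a sentence or two of SAP text, a table note and a little programming. No new data are needed if the pre-dose readings exist; if they do not, the present rule remains and a footnote should say what the change is measured from.
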